## Synopsis of Clinical Study REFLUX

### Protocol summary in English language

**Project Code:**

FW10010127

**Project Title:**

Development of a preparation for supportive supplementation of probiotics in patients with reflux

**Study Title:**

A two-arm, double-blind, randomized, placebo-controlled study investigating the efficacy of a probiotic preparation developed as supportive supplementation of probiotics in patients with reflux.

**Justification for the proposed clinical trial:**

Esophageal reflux, also known as gastroesophageal reflux disease (GERD), is a common condition affecting many adults worldwide. There is evidence that changes in the gut microbiome may influence the symptoms and severity of GERD. Probiotics, capable of restoring balance in the gut microbiota, may provide significant relief from GERD symptoms. This study is designed to assess the efficacy of a probiotic dietary supplement in reducing the adverse effects of GERD, which are also associated with proton pump inhibitor (PPI) therapy.

**Risk/benefit assessment:**

Based on a literature review, probiotic use is generally safe and may provide clinical benefits to patients with gastrointestinal problems. Potential risks associated with the administration of bacterial strains, such as infections in immunocompromised patients, are carefully monitored and minimized through the selection of specific probiotic strains. The benefits include alleviation of GERD symptoms and improved quality of life. Throughout the study, participant safety will be monitored, and all adverse events will be documented and evaluated.

**Investigational product:**

A probiotic dietary supplement containing a blend of probiotic bacteria from the Lactobacillaceae family, and the genera *Streptococcus* and *Bifidobacterium*, selected based on the latest knowledge concerning the use of probiotics in relation to GERD.

**Composition of the probiotic preparation:**

- **Active ingredients:**

- *Lactiplantibacillus plantarum* LP-ONLLY
- *Ligilactobacillus salivarius* LS33
- *Streptococcus salivarius* SAL21
- *Bifidobacterium animalis* subsp. *lactis* HN019
- Guar gum
- Extract from the husk of flaxseeds (*Linum usitatissimum*)

- **Excipients:**

- Soluble corn fiber
- Flavoring
- Steviol glycosides
- Silicon dioxide
- Magnesium stearate

**Placebo:** Placebo tablets contain only the excipients of the dietary supplement.

**Number of study subjects:**

50 subjects will be enrolled (25 patients supplemented with probiotics and 25 patients receiving placebo).

**Purpose of the clinical trial:**

The objective of this trial is to evaluate the effect of the probiotic dietary supplement on the diversity and composition of the gut microbiome in patients diagnosed with GERD who are on PPI therapy. The study will also monitor changes in the oral microbiome and the impact of probiotic supplementation on patient quality of life and GERD symptoms.

**Study design:**

The proposed clinical trial is randomized and double-blinded. It has two arms:

1. Patients supplemented with the probiotic preparation.
2. Patients receiving placebo.

Subjects will be randomized to ensure that neither patients nor physicians know who is receiving probiotics and who is receiving placebo.

**Indication:**

The dietary supplement is intended for patients diagnosed with GERD. The aim of supplementation is to minimize dysbiosis in the gastrointestinal tract caused by the disease itself and/or pharmacotherapy, to reduce reflux-related symptoms, and to improve the quality of life of GERD patients.

**Objectives:**

- **Primary endpoint:**
  - Minimization of dysbiosis in the gastrointestinal tract caused by the disease itself and/or pharmacotherapy.
- **Secondary endpoints:**
  - Reduction of GERD symptoms assessed by standardized questionnaires and changes in symptom scores.
  - Improvement of quality of life assessed by specific questionnaires.
  - Evaluation of safety and tolerability of the preparation.
  - Reduction of gastrointestinal discomfort.

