**Study population:**

- **Inclusion criteria:**
  - Adults aged 40–55 years.
  - Diagnosed GERD.
  - Consent to participate and signed informed consent.
  - Stable health without current complications.

- Patients on stable pharmacological PPI therapy (rabeprazole).
- **Exclusion criteria:**
  - Concurrent participation in another clinical study.
  - Use of probiotics or prebiotics within the last 4 weeks.
  - Pregnancy or breastfeeding.
  - Systemic antimicrobial therapy within the last 4 weeks.
  - Infectious disease of the respiratory or gastrointestinal tract within the last 2 weeks.
  - Serious chronic disease that could affect study results, including cancer, diabetes, inflammatory bowel disease, diagnosed SIBO.
  - Prior surgeries, especially fundoplication and resections of the esophagus or stomach.
  - Patients with psychiatric or cognitive disorders.
  - Hypersensitivity to components of the investigational product.

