### **Statistics:**

Paired comparison of diversity and composition of the microbiome, as well as quantification of probiotic strains from the preparation before the start of the study and after the experimental block, will be conducted using stool samples and oral swabs. Questionnaire results and clinical measurements (endoscopic examination) will be evaluated and correlated with laboratory findings. Comparisons will also be made between the probiotic and placebo groups. A detailed statistical plan will be included in the study protocol.

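### The primary endpoint claims less dysbiosis, and a cause for it, but the measurements stated in the protocol show only that the microbiome changed

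*Protocol*

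**What the plan says.** Four sections of the protocol bear on the point.

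- **Objectives.** The primary endpoint is "Minimization of dysbiosis in the gastrointestinal tract caused by the disease itself and/or pharmacotherapy". The Indication section gives the same aim for the supplement.
- **Purpose of the clinical trial.** The section words its aim as follows: "evaluate the effect of the probiotic dietary supplement on the diversity and composition of the gut microbiome in patients diagnosed with GERD". These patients all take a PPI. No direction of effect is given. Oral microbiome, symptoms and quality of life follow as further items.
- **Statistics.** The first analysis named is "Paired comparison of diversity and composition of the microbiome, as well as quantification of probiotic strains from the preparation", before versus after the experimental phase, in stool and oral swabs. A later sentence adds that the two groups will also be compared, without naming the variable. A detailed statistical plan is promised.
- **Study population and Study design.** Entry requires "Diagnosed GERD" and stable rabeprazole. Both arms are drawn from these patients, 25 in each, and the control arm takes placebo.

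**The concern.** Minimising dysbiosis is a directional statement: a disturbed state exists, and it becomes less disturbed. The endpoint also names the source of the disturbance. Diversity, composition and strain counts can all change without showing either.

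The risk is concrete in this trial. Patients in the active arm swallow live strains, and the same strains are then measured in their samples. Their recovery alone could alter the measured composition. Nothing in the protocol stops such a shift from being reported as success on the primary endpoint, although it would show only that the product was taken and detected. At stake is whether the trial's main conclusion follows from its data.

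**Working it through.** No arithmetic decides this point, and the plan gives no figure to reproduce for it. The check sets what the endpoint claims against what the protocol provides.

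**Step 1. What the claim needs.** To conclude that dysbiosis from GERD or its treatment was minimised, four things are needed: (a) a measure on which one direction means less disturbed; (b) a reference that fixes that direction; (c) a comparison that isolates the supplement's effect; (d) some means of tying the disturbance to the named cause.

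**Step 2. What the protocol supplies.**

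| Needed | Provided in the protocol | Met? |
|---|---|---|
| (a) Directed measure | Diversity, composition and amount of product strains, none with a favourable direction (Statistics) | No |
| (b) Reference | No index, range or reference group; both arms are GERD patients (Study design, Statistics) | Not in this document |
| (c) Comparison isolating the supplement | Randomised, double-blind placebo arm; the between-arm comparison is planned but named after the paired one and without a variable | Available, but not fixed as primary |
| (d) Link to cause | All 50 patients have GERD and all take rabeprazole (Number of study subjects, Study population) | No |

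**Step 3. Direction.** Suppose diversity rises in the active arm relative to placebo, or composition moves. Each patient's own baseline and the placebo arm show that a change occurred. Neither says where normal lies, so the same data fit a move towards it, away from it, or sideways. Choosing a single measure would not settle this by itself, because the favourable direction on that measure would still have to be stated and justified.

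**Step 4. Product strains.** The strains quantified are those in the preparation. More of them in the active arm's stool is what intake would be expected to produce. It reflects exposure and says nothing about a pre-existing disturbance.

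**Step 5. Cause.** Patients without GERD: 50 − 50 = 0. Patients without a PPI: 50 − 50 = 0. With no variation in either presumed cause, no contrast within the trial can attribute a disturbance to GERD, to the drug, or to neither.

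**Step 6. Order of comparisons.** A before-after change within the active arm mixes the supplement's effect with time, diet, study participation and regression to the mean. Only the between-arm difference in change removes these. The Statistics section does not say that this contrast carries the primary endpoint.

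**Step 7. Consistency.** The Purpose section asks whether the supplement affects diversity and composition. The design can answer that. The Objectives section asks whether something abnormal became less so. These are different targets, and only the first matches the listed measurements.

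**The case against.** The best defence is that the protocol text is a synopsis. A dysbiosis index, its reference and its direction commonly sit in a SAP, and none is available here. That stands. It cannot be said that the trial lacks a reference, only that this document fixes a directional endpoint without one. The wording of the primary endpoint, and its mismatch with the stated purpose, remain protocol matters.

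Three stronger readings are tempting, and the documents do not support them.

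- *The entry criteria work against the aim, because dysbiosis is not required and diagnosed SIBO is excluded.* The protocol does require both presumed causes, GERD and rabeprazole, in every patient. SIBO appears only as one example under "Serious chronic disease that could affect study results, including cancer, diabetes, inflammatory bowel disease, diagnosed SIBO", which is ordinary control of confounding. It concerns the small intestine, while the samples are stool and oral swabs, and patients with other dysbiosis remain eligible. A microbiome screen at entry would be a design preference.
- *Patients without dysbiosis dilute the effect and cost power.* The protocol gives no effect size, standard deviation or share of patients with dysbiosis, so any power figure would rest on invented inputs. Dilution also presupposes a directed measure on which such patients cannot improve. That does not fit with the worry that any shift counts as success, which presupposes an undirected one.
- *A microbiome change could never be read as less dysbiosis.* This is too absolute. A directed measure with a reference, fixed in advance and compared between randomised arms, would permit that reading with no entry criterion at all.

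Nor is the randomised comparison biased. A between-arm difference would be a real effect of the product; the label put on it is what is open to question.

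**Conclusion.** The point holds as a mismatch between the primary endpoint and the measurements stated for it. The trial can show that the supplement changed the gut microbiome relative to placebo. As specified in the protocol, it cannot show that the change was towards normal, or that a disturbance due to GERD or PPI treatment was reversed.

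The size is qualitative: it concerns the primary conclusion for all 50 patients, and no numerical loss can be derived from the document. The direction part of the conclusion assumes that no directed, reference-based measure is fixed elsewhere before unblinding. If a SAP does so, that part is resolved. The attribution to GERD or drug treatment would remain untestable, because it depends on who is enrolled and not on how the data are analysed.

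**What to change.** 1. Restate the primary endpoint to match the Purpose section: the between-arm difference in change from baseline to week 6 (the end of supplementation) of one prespecified stool microbiome measure, adjusted for its baseline value. Stool fits because the stated purpose concerns the gut microbiome, with the oral microbiome as a further item.
2. In the Statistics section, name this between-arm contrast as primary and make the paired within-arm comparisons descriptive.
3. State that recovery of the administered strains is evidence of exposure and does not count as reduced dysbiosis.
4. Remove the attribution to GERD or drug treatment from the endpoint. It can stay as background rationale.
5. Keep the term dysbiosis in the primary endpoint only if a directed measure, with its reference, is fixed before unblinding.

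The cost is protocol and SAP wording. The samples are already planned before and after supplementation, so items 1 to 4 need no extra patients or visits; item 5 adds the work of choosing and justifying a reference. The downside is a narrower primary claim, an effect on the gut microbiome versus placebo, if no usable reference exists.

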### **Study plan and schedule:**

- Study initiation: Week 1
- Experimental phase: 6 weeks
- Follow-up evaluation: Immediately after supplementation ends

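### The primary endpoint is an aim rather than a measurable variable, and nothing in the protocol summary picks the one measure, site and comparison that decides the trial

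*Protocol*

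**What the plan says.** Four sections of the Protocol bear on the primary endpoint.

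- **Objectives.** The single primary endpoint is "Minimization of dysbiosis in the gastrointestinal tract caused by the disease itself and/or pharmacotherapy". Dysbiosis is not defined there or elsewhere, and no index, composition measure or criterion for success is given.
- **Purpose of the clinical trial.** The objective is to "evaluate the effect of the probiotic dietary supplement on the diversity and composition of the gut microbiome". The next sentence adds: "The study will also monitor changes in the oral microbiome". This puts the gut first and the mouth second.
- **Statistics.** The planned analysis is "Paired comparison of diversity and composition of the microbiome, as well as quantification of probiotic strains from the preparation", before and after the experimental block, and it "will be conducted using stool samples and oral swabs". The randomized comparison comes later: "Comparisons will also be made between the probiotic and placebo groups". None of these is marked as primary. The section leaves the detailed statistics to the study protocol.
- **Study plan and schedule.** Timing is clear: "Follow-up evaluation: Immediately after supplementation ends", after a six-week experimental phase.

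The text at hand is headed as a synopsis and described as an English-language summary of the protocol.

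**The concern.** A primary endpoint has to be something that can be computed for each patient and then compared. The wording in Objectives almost restates the aim of supplementation given under Indication. As worded it cannot be observed either: every enrolled patient has GERD and takes a PPI, and the only comparator is placebo, so the trial has no group that shows which part of any dysbiosis the disease or the drug caused.

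The choice of variable is therefore open once data exist. Diversity might move while composition does not, or a before/after change in the probiotic arm might appear without a difference from placebo. Any of these could be presented as the primary result. The before/after comparison is a particular risk because it is listed first, and a change over six weeks within one arm does not separate the product from time, diet or regression to the mean. No result is named in advance whose failure would make the trial negative.

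**Working it through.** **The plan's own figure.** The only design figure is the sample size: "50 subjects will be enrolled (25 patients supplemented with probiotics and 25 patients receiving placebo". No significance level, power, effect size or standard deviation accompanies it, so it cannot be reproduced.

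**Inputs**

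| Input | Value | Source |
|---|---|---|
| Microbiome measures | 3 (diversity, composition, strain quantification) | Statistics |
| Body sites | 2 (stool, oral) | Statistics |
| Types of comparison | 2 (before/after, between arms) | Statistics |
| Measures in the stated objective | 2 (diversity, composition), gut only | Purpose |
| Patients per arm | 25 | Number of study subjects |
| Significance level per test | 0.05, two-sided | **Assumed**; not stated |

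**Step 1: count the candidate results** (one test per measure, site and type of comparison)

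- Narrowest reading (gut only, diversity and composition, between arms): 2 × 1 × 1 = 2.
- The same with before/after tests also eligible: 2 × 1 × 2 = 4.
- Broad reading of Statistics (all measures, both sites, one type of comparison): 3 × 2 × 1 = 6.

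No reading of the text leaves one.

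**Step 2: chance of at least one false positive.** With k independent tests at 0.05 and no true effect, this is 1 − 0.95^k.

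| k | Formula | Result |
|---|---|---|
| 1 | 1 − 0.95 | 5.0% |
| 2 | 1 − 0.9025 | 9.8% |
| 4 | 1 − 0.8145 | 18.5% |
| 6 | 1 − 0.7351 | 26.5% |

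**Step 3: allow for correlation.** Microbiome measures on the same patients are unlikely to be independent. For six equally correlated normal test statistics (simulation, 200,000 draws), the chance is 24.1% at correlation 0.3, 20.8% at 0.5 and 13.9% at 0.8. Positive correlation would also lower the figures for two and four tests. All stay above 5% unless the tests are fully redundant.

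**Step 4: what keeping six co-equal tests would cost.** A Bonferroni split gives 0.05 / 6 = 0.0083 per test. The standardized difference detectable with 80% power at 25 per arm (normal approximation, no dropout) is (z for the two-sided level + 0.842) × √(2/25):

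- One test: (1.960 + 0.842) × 0.283 = 0.79 SD.
- Six tests: (2.638 + 0.842) × 0.283 = 0.98 SD.

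Power at a true difference of 0.8 SD falls from 81% to 58%. Correcting for multiplicity is thus a poor substitute for choosing one variable in a trial of 50.

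**The case against.** The strongest reply is that this is a summary. It says that statistical detail will appear in the study protocol, which is not at hand and may name the index, the contrast and the significance level. This stands as a limit on certainty: a reader might infer that the trial has no confirmatory test anywhere, and the text shown cannot support that. It does not remove the point. The primary variable is protocol content rather than a detail for a statistical analysis plan, and a summary that states a primary endpoint should state a measurable one.

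Four stronger readings are tempting and should be resisted.

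- *At least six results are open.* Six is the broad reading, not a floor. Purpose already ranks the gut ahead of the mouth, and Statistics can be read as a list of assays that does not disturb that ranking. Strain quantification reflects intake of the product. It is expected to differ between arms whether or not dysbiosis changes, so it sits badly in a false-positive calculation. Without it and the oral swabs, two to four candidates remain. Counting both types of comparison at both sites for all three measures would give 12 tests and 46.0%, but that total rests on the same weak members.
- *The time point is missing.* It is absent only from the endpoint wording. Supplementation, Statistics and the schedule together fix one assessment before the start and one at the end of six weeks.
- *A negative trial could hardly be declared.* With an error rate of 21% to 26%, some 74% to 79% of trials without any effect would show none of six tests significant. What is missing is the named result that would count as failure.
- *A stated 5% error rate is broken.* The document sets no rate, so the percentages illustrate an assumed one.

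**Conclusion.** The point holds in this form: the primary endpoint is an aim, and this protocol summary selects no single measure, site or contrast to stand for it. Followed as written, the analysis leaves between two and six candidate primary results for one type of comparison, or four if both types are allowed for the two gut measures. The chance of a false-positive primary claim then runs from about 10% through 19% to 26%, and is 21% to 24% for six tests at correlations of 0.5 to 0.3. These figures assume a two-sided 5% test for each candidate and no effect on any of them; the first three also assume independence. The defect in the wording does not depend on these figures. It should be corrected before the data are analysed, unless the full protocol already settles it.

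**What to change.** Replace the primary endpoint in Objectives with one stool-based variable. One example is the Shannon diversity index at the end of the six-week supplementation, compared between probiotic and placebo and adjusted for the baseline value. The sponsor may prefer another stool measure. What matters is that there is one, with the direction that counts as improvement and the significance level stated.

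Then say in both Objectives and Statistics that:

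- the other stool measures, the oral microbiome and the before/after comparisons within an arm are secondary or exploratory;
- strain quantification is an exposure check and not evidence of reduced dysbiosis.

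If the full protocol already names such a variable, align the summary with it.

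The cost is wording only, with no change to sampling, visits or sample size. The downside for the sponsor is that primary success can no longer be claimed on a different microbiome measure.

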**Study population:**

- **Inclusion criteria:**
  - Adults aged 40–55 years.
  - Diagnosed GERD.
  - Consent to participate and signed informed consent.
  - Stable health without current complications.

- Patients on stable pharmacological PPI therapy (rabeprazole).
- **Exclusion criteria:**
  - Concurrent participation in another clinical study.
  - Use of probiotics or prebiotics within the last 4 weeks.
  - Pregnancy or breastfeeding.
  - Systemic antimicrobial therapy within the last 4 weeks.
  - Infectious disease of the respiratory or gastrointestinal tract within the last 2 weeks.
  - Serious chronic disease that could affect study results, including cancer, diabetes, inflammatory bowel disease, diagnosed SIBO.
  - Prior surgeries, especially fundoplication and resections of the esophagus or stomach.
  - Patients with psychiatric or cognitive disorders.
  - Hypersensitivity to components of the investigational product.

### **Supplementation:**

Patients will take the probiotic preparation, 2 tablets twice daily (morning before meals and evening after meals). The experimental phase will last 6 weeks. Patients in the control arm will receive placebo. Supplementation will be discontinued if adverse effects occur.

